10.6 Sample Size

Since there is no predicate data in the United States we have elected to do a pilot study involving 70 patients and up to 30 volunteers who will help the investigators optimize the technique with the MCC and MCC-T. We will allocate patients to MCC or MCC-T randomly using a randomization protocol generated by Redcap

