Exclusion Criteria	
 1. Patient with dysphagia. 2. Patient with previous intestinal surgery. 3. Patient with Crohn's disease or other potential obstructive conditions, unless there is a recent CTE, MRE or patency capsule performed to exclude an obstructive lesion that may retain the capsule. 4. Female patient who is pregnant. 5. Patient with implanted medical device that would be potentially affected by magnets or radiofrequency emissions (e.g., pacemakers, implanted cardiac defibrillators). 6. COVID-19+ or with symptoms consistent with the infection. Fever, new cough, myalgias, and chills
Study Population and Sample Size	Since there is no predicate data in the USA, we plan a pilot study with 100 patients and 10 volunteers to help optimize the use of the MCC and MCC-T

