5.2 Patient Population

Approximately 400 patients a month are seen in the UMass Gastroenterology outpatient clinic or are referred for EGD with complaints of upper abdominal pain requiring an upper endoscopy. These patients will be screened for possible inclusion in the study the day prior to their visit to the clinic.

A total of up to 100 patients will be enrolled in the study, including up to 30 healthy volunteer participants for training.

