5.8 Screening Failure

Patients who have not fulfilled all the inclusion criteria or have fulfilled one of the exclusion criteria will not be included in this study. Screening failures will be replaced by suitable candidates.

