10.2 Study Populations

The safety population will include all subjects who swallowed the NaviCam Capsule with tether and underwent upper endoscopy. All safety and efficacy analyses will be performed on the safety population.

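### The synopsis plans 100 patients plus 10 volunteers (110 people), while sections 5.2 and 10.6 plan at most 100 people, 70 of them patients under 10.6; no calculation supports either figure

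*Combined protocol and SAP*

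**What the plan says.** Three places in the combined protocol and SAP give the sample size.

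- Study Synopsis, row on study population and sample size: "we plan a pilot study with 100 patients and 10 volunteers".
- Section 5.2: "A total of up to 100 patients will be enrolled in the study, including up to 30 healthy volunteer participants for training".
- Section 10.6: "we have elected to do a pilot study involving 70 patients and up to 30 volunteers".

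The only basis offered is in section 10.6: "Since there is no predicate data in the United States we have elected to do a pilot study". The same section adds "We will allocate patients to MCC or MCC-T randomly using a randomization protocol generated by Redcap", without an allocation ratio.

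Section 10.2 defines a single analysis set: "The safety population will include all subjects who swallowed the NaviCam Capsule with tether and underwent upper endoscopy". It continues: "All safety and efficacy analyses will be performed on the safety population". Section 6.7 grades each finding D0, D1 or D2 by how likely it is to explain the patient's presenting complaint. Sections 4.2 and 10.5 count D2 as positive for the primary effectiveness endpoint. Safety is also a primary endpoint in section 4.2.

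**The concern.** The synopsis and the body of the protocol give different numbers of symptomatic patients. Both primary endpoints are estimated from those patients, so the recruitment target, the size of the randomised groups and the width of every interval depend on which page is followed. In a powered trial the intended number could be recovered from the calculation behind it. Here there is none.

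A smaller matter goes with it. Section 5.2 counts healthy volunteers inside a total that it calls patients, and section 10.2 admits all subjects who had both procedures. The plan never says whether a volunteer can enter the accuracy analysis, although the D0–D2 scale has no meaning for someone without a presenting complaint.

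**Working it through.** **1. Arithmetic between the statements**

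| Place | Patients | Volunteers | Total |
|---|---|---|---|
| Synopsis | 100 | 10 | 100 + 10 = 110 |
| Section 5.2 | total minus volunteers: 70 if 30, 90 if 10 | up to 30 | up to 100 |
| Section 10.6 | 70 | up to 30 | up to 70 + 30 = 100 |

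Section 10.6 reproduces the cap in section 5.2 (70 + 30 = 100). The synopsis fits neither: its 110 exceeds the cap, and its 100 patients are not the 70 of section 10.6. The differences are 100 − 70 = 30 patients, up to 30 − 10 = 20 volunteers, and at least 110 − 100 = 10 people in total.

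**2. Can either figure be derived?** No. The documents give no significance level, power, effect size, discordance rate, margin or dropout allowance, so neither 70 nor 100 can be reproduced.

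**3. What the difference does to precision**

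*Sensitivity.* Assume that 30% of patients have a D2 finding (the documents give no prevalence). Reference-positive patients are 0.30 × 70 = 21 or 0.30 × 100 = 30. Take a sensitivity near 86%: 18/21 = 85.7% and 26/30 = 86.7%. The Clopper–Pearson limits are the 2.5% point of Beta(x, n − x + 1) and the 97.5% point of Beta(x + 1, n − x).

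- 18/21: 63.7% to 97.0%
- 26/30: 69.3% to 96.2%

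To show the range over prevalence, the Wald half-width at an assumed sensitivity of 90% is 1.96 × √(0.9 × 0.1 / m), with m the number of reference-positive patients.

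| Assumed prevalence | 70 patients | 100 patients |
|---|---|---|
| 20% | m = 14, ±15.7 points | m = 20, ±13.1 points |
| 30% | m = 21, ±12.8 points | m = 30, ±10.7 points |
| 50% | m = 35, ±9.9 points | m = 50, ±8.3 points |

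*Safety.* With no adverse events in n subjects, the upper limit of the exact two-sided 95% interval is 1 − 0.025^(1/n): 5.1% for n = 70 and 3.6% for n = 100.

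*McNemar's test.* Assume two-sided alpha 0.05 and discordant proportions p10 and p01, with d = p10 − p01 and s = p10 + p01. Approximate power is Φ[(d√N − 1.96√s) / √(s − d²)].

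| Assumed p10, p01 | N = 70 | N = 100 |
|---|---|---|
| 20%, 5% | 72% | 86% |
| 15%, 5% | 46% | 61% |
| 20%, 10% | 33% | 45% |

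**4. Effect of section 10.2.** The figures above use all planned patients. Read literally, section 10.2 keeps only those who swallowed the tethered capsule and had EGD. If allocation were 1:1 (an assumption), that would be 35 of 70 or 50 of 100, and the zero-event upper limit would be 10.0% or 7.1%.

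**5. Volunteers.** Sections 5.2 and 10.6 give them a training and technique role. Sections 4.2 and 10.5 define the primary endpoint in patients with upper abdominal pain, which points to their exclusion. Section 10.2 nevertheless takes all subjects with both procedures and has no exclusion line.

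**The case against.** The strongest reply is that this is a pilot with no power calculation, so no powered conclusion rests on 70 rather than 100. The sensitivity intervals are wide under either number, and the repair is editorial. That is fair as to the size of the consequence. It does not remove the need for one enrolment target, particularly as section 10.5 plans a significance test and effectiveness and safety are both primary.

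Several stronger readings are tempting, and the documents do not support them.

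- *That there are three incompatible sample sizes.* Sections 5.2 and 10.6 agree at 70 + 30 = 100. Section 5.2 is only looser, because it sets upper limits. The conflict is the synopsis against the body.
- *That 70 or 100 is the number that will be analysed.* These are planned patients. Section 10.2 restricts the analysis set further, and section 10.7 uses available data only.
- *That section 5.8 bars the volunteers.* It says "Patients who have not fulfilled all the inclusion criteria or have fulfilled one of the exclusion criteria will not be included in this study", which concerns patients at screening. The synopsis and sections 5.2 and 10.6 expressly provide for volunteers. Separate eligibility wording for them would help, but its absence is not a prohibition.
- *That volunteers will inflate negative predictive value.* No passage says that volunteers undergo EGD, which section 10.2 requires, and a volunteer without a D grade would have no result to count. No size can be put on this. What stands is that a volunteer who did have both procedures is not expressly kept out.
- *That the arms are 35 and 35.* Section 10.6 gives no ratio, so any such split is an assumption.

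**Conclusion.** The point holds as a contradiction between the synopsis and the body of the protocol. The planned number of patients is 100 in one and 70 in section 10.6, so at least one statement is wrong, and the documents do not show which. The step counts (30 patients, up to 20 volunteers, at least 10 people in total) need no assumption.

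The statistical effect is moderate. At the assumed prevalence, the lower limit for sensitivity moves by about 5 to 6 points (63.7% against 69.3%), and the zero-event safety bound by 1.5 points (5.1% against 3.6%). These figures rest on the assumed 30% prevalence, a sensitivity near 86%, and all planned patients being analysed. The volunteer issue is a gap in the definition of the analysis set, not a demonstrated bias.

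**What to change.** 1. Put one set of numbers in the synopsis, section 5.2 and section 10.6, with randomised patients and training volunteers counted separately. If section 10.6 governs, this is 70 randomised patients plus up to 30 volunteers not counted in the 70. If the synopsis governs, the cap in section 5.2 and the figures in section 10.6 must change to match.
2. In section 10.6, state the allocation ratio and the expected interval width for the chosen number, with the prevalence assumed and on the analysis set that section 10.2 actually defines.
3. In section 10.2, state that volunteers are excluded from the accuracy, kappa, completion and satisfaction analyses, because D0–D2 depends on a presenting complaint that they do not have. Say whether they enter the learning-curve analysis and the adverse event listings.

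The cost is protocol wording in four places. If section 10.6 is the intended version, the patient number in the synopsis falls from 100 to 70. If the synopsis is, the site must recruit 30 more patients than section 10.6 plans.

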10.7 Handling of Missing Data

Missing data will not be imputed. Analysis will be conducted on available data only.

10.8 Monitoring Plan

Monitoring functions shall be performed in compliance with Good Clinical Practice per ISO 14155:2011, and as outlined in 21CFR§821.43(d) and 21CFR§812.46.

ANX Robotica will appoint Clinical Monitors for this study. The Clinical Monitors should be qualified by training and experience to oversee the conduct of the study. The Clinical Monitor's responsibilities include maintaining regular contact with the investigational site, through telephone contact and on-site visits, to ensure that: 1) the study protocol is followed; 2) complete, timely, and accurate data are gathered; 3) problems with inconsistent and incomplete data are addressed; and 4) complications and Unanticipated Adverse Device Effects are reported to the Sponsor.

10.9 Device Accountability

ANX Robotica will provide the site with one NaviCam System as well as capsules and tethered devices sufficient to perform the required number of procedures. The system as well as its various components will be marked "for investigational use" and the investigators are responsible for storing all investigational device components in a secure place to avoid unauthorized use. Immediately upon completion of the study the system and unused items will be returned to ANX Robotica.

11 PUBLICATION POLICY

Any presentation/publication of complete/partial study data by the Investigator or any other party is stipulated by written authorization from the sponsor.

12 ADMINISTRATIVE PROCEDURES OF THE INVESTIGATION

12.1 Audit and Supervision

The investigators, the site and study documentation may be subject to Quality Assurance audits during the course of the study. In addition, inspections may be conducted by regulatory bodies at their discretion, during and after study completion.

12.2 Reporting of Results

The study results will be summarized and presented in the study report according to the ISO 14155 standard and 21 CFR 812.150.

The investigators will be able to publish and/or present the data generated from the study after mutual written agreement between the Investigator and Sponsor.

12.3 Criteria for Removal from the Study

The investigator may withdraw subjects from the study as is deemed necessary or deemed to be in the best interests of the subject, such as,

- continued noncompliance with the protocol or study visits,
- severe illness or disability during the study for non-study issues,
- pursuit of subsequent alternative treatment for the same condition, or
- development of intolerable side effects where continued follow-up becomes too burdensome.

In addition, a subject may also choose to exit the study at any time but will be strongly encouraged to participate in the follow-up telephone call for safety reasons.

13 APPLICABLE DOCUMENTS

1. 21 CFR 812, Investigational Device Exemption
2. ISO 14155:2011, Clinical investigation of medical devices for human subjects -- Good clinical practice
3. FDA guidance “Adaptive Designs for Medical Device Clinical Studies” (July 27, 2016).

15 APPENDICES

- 1. Appendix I: Patient satisfaction questionnaires**
- 2. Timeline - Appended**
- 3. NSR letter from FDA**

Appendix I: Patient Satisfaction Questionnaires

1. Please tell us on a score of 1 to 10 your preference for the magnetic capsule test or magnet on a string test, with 1 being the least liked and 10 the best:

1	2	3	4	5	6	7	8	9	10
---	---	---	---	---	---	---	---	---	----

2. Please tell us on a score of 1 to 10 your preference for the upper endoscope, with 1 being the least liked and 10 the best:

1	2	3	4	5	6	7	8	9	10
---	---	---	---	---	---	---	---	---	----

3. Was there anything you particularly liked about the magnetic capsule test or magnetic capsule on a string test: _____

4. Was there anything you particularly disliked about the magnetic capsule test or magnetic capsule on a string test: _____:

5. Was there anything you particularly liked about the upper endoscopy test: _____

6. Was there anything you particularly disliked about the upper endoscopy test: _____

7. Did you have any problems with the magnetic capsule or magnetic capsule on a string test at the time of the test: _____

8. Did you have any problems with the magnetic capsule or magnetic capsule on a string test after the test: _____

9. Did you have any problems with the endoscopy test at the time of the test: _____

10. Did you have any problems with the endoscopy test after the test: _____

Timeline for MCC v EGD Pilot study
